8. TECHNICAL DETAILS

Include a brief statement of: study-specific documents used, including version numbers; which software package or packages used; and the directory/file paths used to store data, code and output documents.

Describe what quality assurance measures are in place to monitor the quality of any coding. Document who will review which pieces of code, and to what level of detail. For example:

A second review statistician will independently reproduce the primary analyses. The reviewing statistician will have an overview of the entire.

9. SUMMARY OF CHANGES TO THE PROTOCOL

On December 17, 2018, the AZENT data monitoring committee, on review of the interim analysis, determined that there was evidence to support continued accrual, however the trial was closed to further accrual due to a funder's decision.

Appendix 1. Handling of missing date and time fields

All dates and times used in the analysis are supposed to be complete. Nevertheless, in certain situations it will be difficult or impossible to have a complete date or time, e.g., lost to follow-up patients. SAP Table 3 contains a list of dates/times that will be completed in case of missing information.

General rules for completion of dates are the following:

1. Dates are split in 3 parts: year, month and day. Year is the top level, month is medium level and day is low level. If a part expected to contain a number is numeric but the value is outside a valid range, the complete date is handled as missing. For example, if date = 32-NOV-2012 the whole date is considered to be missing.
2. If a part expected to contain a number is not numeric, i.e., contains values such as, for example, ND, NA, 2? it is considered as missing.
3. If a part is missing, all other parts of a lower level are considered to be missing, e.g., '21-ND-2012' is considered as 'NK-NK-2012'.
4. Missing parts are changed into acceptable non-missing values depending on the type of date to be replaced.

In the following table, 'lower limit' and 'upper limit' refer to the minimum or maximum, respectively, of a possible date. For example, if the day is missing, the lowest limit is the first day of the given month and the upper limit is the last day of the given month. If the day and month are missing, the lower limit refers to the first day of the given year and the upper limit to the last day of the given year. The earliest and the latest of different dates refer to the first or last date, respectively, when ordered in sequence.

SAP Table. 2 Handling of missing data and time fields

Type of Date / Time	Date / Time is incomplete	Date / Time is missing
Date of birth	Day missing: 15 th of the month Day and month missing: 30 th of June	No replacement
AE resolution date	The upper limit	No approximation, the AE is considered as ongoing in the analysis.
AE onset date	If the end date of the AE is not before the start of study drug, and if the study drug start falls in the range of possible dates, it is the study drug start date. In all the other cases, it is the lower limit.	Earliest date between the AE end date and the start of study drug.
Hospitalization discharge date	The upper limit	No approximation, the hospitalization is considered as ongoing in the analysis.
Hospitalization admission date	If the onset date of the AE leading to hospitalization falls in the range of possible dates, it is the onset date of the AE. In all the other cases, it is the lower limit.	The onset date of the AE leading to hospitalization

Previous/concomitant medication start date	
Lower limit except when:
 
Not tagged as ongoing at baseline
 
AND
 
Medication stop date not collected or with the upper limit after the study drug start
 
AND
 
the treatment start day falls in the range of possible dates.
 
In which case it is the study drug start day
	No replacement, the medication is considered to have started before the study
Previous/concomitant medication end date	
Upper limit except when:
 
Medication start is before study drug start or missing
 
AND
 
Upper limit is after the study drug start
 
AND
 
Not tagged as concomitant at baseline.
 
In which case it is 1 day before study drug start
	No replacement (considered ongoing)
End of treatment	
Use the earliest date between the:
 
 • upper limit • last contact date • date of death (if applicable) 	
Use the earliest date between the:
 
 • last contact date • date of death (if applicable)
Death date	Use the lower limit	No replacement

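### SAP Appendix 1 blanks the whole date when one numeric part is out of range, so a death recorded with month and year can have no usable date while a death known only to the year is imputed

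*SAP*

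**What the plan says.** SAP Appendix 1 expects dates to be complete and gives fallback rules for those that are not.

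- **Rule 1 (numeric but impossible part).** If "the value is outside a valid range, the complete date is handled as missing". The worked example is an impossible day: "For example, if date = 32-NOV-2012 the whole date is considered to be missing".
- **Rule 2 (non-numeric part).** A part that "contains values such as, for example, ND, NA, 2? it is considered as missing". Only that part is lost.
- **Rule 3 (cascade).** "If a part is missing, all other parts of a lower level are considered to be missing". The loss runs downward only. The SAP's own example, with day 21 and an unknown month in 2012, keeps the year.
- **Lower limit.** "if the day is missing, the lowest limit is the first day of the given month"; with day and month both missing it is the first day of the year.
- **SAP Table 2, death date.** Incomplete: "Use the lower limit". Missing: "No replacement".
- **SAP Table 2, end of treatment.** Incomplete: the earliest of the upper limit, last contact and, if applicable, death. Missing: the earliest of last contact and, if applicable, death.

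SAP section 5.2.2 measures OS to death from any cause. It counts a death in PFS or DOR only where no progression was documented. Section 5.2 refers censoring to an external guidance, and section 7.6 discusses censoring only for withdrawn patients. Neither says how a recorded death without a date is handled.

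**The concern.** The rules treat a more informative entry worse than a less informative one. An impossible day beside a valid month and year leads to nothing being used, while a date with no known day or month is imputed from the year alone. For most variables this is a nuisance. For a death date it matters, because Table 2 imputes one class and leaves the other blank.

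A Kaplan-Meier analysis needs a time for each event. A patient recorded as dead but with a blanked date cannot contribute a timed death, and the SAP leaves the programmer to choose between excluding and censoring. Both choices lose a known death. The choice of the lower limit for incomplete death dates is cautious, since it takes the earliest possible date; rule 1 works against that caution.

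**Working it through.** The SAP gives no figure on this point, so there is none to reproduce. The check applies the written rules to test dates and then shows the size on stated assumptions.

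**Step 1. The rules applied to a death date**

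| Entry | Rule | After the rule | Table 2 result | Span of possible dates |
|---|---|---|---|---|
| ND-NOV-2012 | 2, 3 | NK-NOV-2012 | 01-NOV-2012 | 29 days |
| 2?-NOV-2012 | 2, 3 | NK-NOV-2012 | 01-NOV-2012 | 29 days |
| 21-ND-2012 | 2, 3 | NK-NK-2012 | 01-JAN-2012 | 365 days |
| 32-NOV-2012 | 1 | wholly missing | no date | not applicable |

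If the out-of-range day were treated as a missing day, the last row would match the first: 01-NOV-2012, with a span of 29 days.

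An entry such as 31-NOV is unclear. Rule 1 splits the date and tests each part; 31 is valid as a day taken alone, and the SAP's only example is 32. The SAP does not say whether the day is checked against its month.

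**Step 2. Which endpoints are exposed**

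- OS: any death with a blanked date.
- PFS: only if no progression was documented earlier. A patient with an earlier progression date keeps the PFS event.
- DOR: the same condition, among responders.

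**Step 3. Size for survival**

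Inputs: N = 21 is the planned first stage (SAP section 6.4). SAP section 9 says accrual closed after the interim analysis but gives no final number, so 21 is an assumption. Also assumed: 8 deaths, no other censoring, one death affected.

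- All deaths counted: (21 − 8)/21 = 13/21 = 61.9%.
- Affected patient excluded: (20 − 7)/20 = 13/20 = 65.0%.
- Affected patient censored after the last death: (21 − 7)/21 = 14/21 = 66.7%.
- Affected patient censored after k of the other 7 deaths: [(21 − k)/21] × [13/(20 − k)]. This is 65.0% at k = 0 and 66.7% at k = 7, so censoring always falls within that range.

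The shift is 3.1 to 4.8 percentage points, from losing 1 of 8 events (12.5%). With 28 deaths in the planned 73 patients, also assumed, the figures are 45/73 = 61.6%, 45/72 = 62.5% and 46/73 = 63.0%.

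The upward shift applies from the time of the affected death onward. Before it, exclusion gives a slightly lower curve: (20 − k)/20 against (21 − k)/21 after k other deaths.

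**Step 4. End of treatment**

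Let U be the upper limit of the recorded month, L last contact and D death.

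- Incomplete date: min(U, L, D).
- Missing date: min(L, D).

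The two differ only if min(L, D) > U, that is, if both last contact and death fall after the recorded month (last contact alone if the patient has not died). Only then does rule 1 lengthen TTF or exposure.

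**The case against.** The strongest defence is that an impossible value proves an entry error without showing which part is wrong. A recorded 31-NOV might be 30-NOV, 31-OCT or 31-DEC, whereas an unknown-day code says honestly that only the day is unknown. Distrusting the whole entry is a recognisable convention, and keeping the month could place a death in the wrong month. This stands as a cost of the fix. It does not justify leaving a known death undated when the same table accepts a span of up to a year for a death known only to the year.

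An impossible date is also visible and correctable, so it should normally be queried before database lock. That stands too: the rule matters only for what remains unresolved, although that residue is what Appendix 1 exists for.

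A reader might infer that the SAP drops such patients from OS and PFS, or censors them. It says neither. Leaving a date unreplaced fills in nothing; it does not settle the patient's status, and section 5.2 sends censoring to a guidance outside the documents. What the text supports is narrower: under the written rules the death has no time at which it can count. For PFS even that fails if progression was documented earlier.

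The number of deaths and the frequency of impossible dates are not in the documents, so the percentages illustrate size and do not predict it.

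**Conclusion.** The inconsistency is real and lies in the SAP's own rules and example. A recorded death with an out-of-range day ends with no date, and cannot be a timed event in OS, or in PFS or DOR without earlier documented progression. The SAP does not say what happens to the patient next, and either available choice raises final survival.

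The point is minor. It should arise rarely, and it concerns secondary efficacy analyses that SAP sections 7.2 and 7.8 call exploratory. The primary endpoint, confirmed response, uses neither a death date nor an end-of-treatment date, so the two-stage decision rule is untouched. A reader might take 66.7% as the effect of one lost death; it is only the top of a range that starts at 65.0%, and the whole range rests on the assumed 8 deaths in 21 patients with no other censoring.

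**What to change.** 1. Reword rule 1 so that an out-of-range part is treated as missing at its own level, with lower levels also missing and valid higher levels kept (32-NOV-2012 becomes NK-NOV-2012). Apply the same to impossible day-month combinations such as 31-NOV, after a data query. Then apply Table 2.
2. Add that an imputed death date may not be earlier than the last date on which the patient was known to be alive.
3. For a recorded death with no usable date at all, keep the patient in OS as an event at a stated date, for example the day after last known alive, and report how many such cases there are. State the corresponding handling for PFS and DOR where no progression was documented.

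The cost is a few sentences in the SAP and a small programming change. The downside is that an imputed month may be wrong when the entry error lies in the month; querying first and reporting the count keep that visible.

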Serious concomitant systemic disorder, including conditions that could interfere with absorption	Investigational Medicinal Product	No	Case by case	No
IMP overdose	Investigational Medicinal Product	No	Case by case	No
IMP underdose	Investigational Medicinal Product	No	Case by case	No
IMP administration dosing/schedule	Investigational Medicinal Product	No	Case by case	No
IMP toxicity	Investigational Medicinal Product	No	Case by case	No
Tumor assessment not done	Efficacy	No	Yes	No
Tumor assessment out of the window	Efficacy	No	Case by case	No
No baseline tumor assessment	Efficacy	No	Yes	No
No post-baseline tumor assessment	Efficacy	No	Yes	No
Subject not withdrawn as per protocol	Safety	No	Case by case	No

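### The SAP rule for incomplete medication end dates has no range check, so a stop month recorded after first dose can be replaced by the day before first dose

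*SAP*

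**What the plan says.** SAP Appendix 1 (SAP Table 2) sets the rules for partial dates. The upper limit is the latest date compatible with what was recorded: if only the day is missing, "the upper limit is the last day of the given month". An incomplete medication end date takes that upper limit unless three conditions all hold:

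- "Medication start is before study drug start or missing"
- "Upper limit is after the study drug start"
- "Not tagged as concomitant at baseline"

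The outcome is then fixed: "In which case it is 1 day before study drug start".

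The medication start-date row just above also has an exception tied to first dose, but one of its conditions is that "the treatment start day falls in the range of possible dates". The AE onset row carries the same safeguard. For a medication start date that is missing altogether, the table says: "No replacement, the medication is considered to have started before the study". An end date that is missing altogether leaves the medication as ongoing.

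General rule 4 of the same appendix provides for the missing parts of a date to be filled in. It does not provide for recorded parts to be changed.

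**The concern.** The exception looks designed for an ambiguous record: the stop month or year contains first dose, and an untagged drug with an early or unknown start is assumed to have ended before treatment began. As written it reaches further. The second condition tests only the latest possible stop date, and that test is also passed when every possible stop date is after first dose. In that case the recorded month or year already shows use on study, and the rule replaces it with a pre-dose date.

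The natural trigger is a drug begun on study whose start date was not recorded. It is correctly untagged at baseline, it is deemed to have started before the study, and a partial stop date then gives it a pre-dose end.

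Two outputs could be affected. SAP 7.3 describes concomitant medications as part of the safety analysis. SAP Appendix 2 lists prohibited concomitant medication as a deviation that is judged case by case for the per-protocol set.

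**Working it through.** The plan gives no figure to reproduce, so the check applies the rule as written to test records. First-dose dates are illustrative. Two readings are assumed: the start-date row is applied before the end-date row, and the baseline tags named in the two rows are the same tag.

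Let D be first dose, and L and U the earliest and latest possible end dates.

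- Rule as written: if (start missing or start < D) and U > D and no baseline tag, then end = D − 1; otherwise end = U.
- The imputed date falls outside the recorded range when L > D − 1, by L − (D − 1) days.

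**Example.** D = 10-JAN-2018, start missing, no tag, stop NK-JUN-2018. Then L = 01-JUN-2018 and U = 30-JUN-2018. The start is missing, U is after D and there is no tag, so the end date becomes 09-JAN-2018. The gap to 01-JUN-2018 is 22 + 28 + 31 + 30 + 31 + 1 = 143 days.

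**Further records, D = 10-MAR-2018.** The last column adds the condition L ≤ D ≤ U to the exception.

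| Start | Tag | Stop | End as written | Days before L | End with range condition |
|---|---|---|---|---|---|
| missing | no | NK-AUG-2018 | 09-MAR-2018 | 145 | 31-AUG-2018 |
| 01-FEB-2018 | no | NK-AUG-2018 | 09-MAR-2018 | 145 | 31-AUG-2018 |
| NK-NK-2017 (set to 01-JAN-2017) | no | NK-AUG-2018 | 09-MAR-2018 | 145 | 31-AUG-2018 |
| missing | no | NK-NK-2019 | 09-MAR-2018 | 298 | 31-DEC-2019 |
| missing | no | NK-MAR-2018 | 09-MAR-2018 | in range | 09-MAR-2018 |
| missing | no | NK-NK-2018 | 09-MAR-2018 | in range | 09-MAR-2018 |
| 01-FEB-2018 | yes | NK-AUG-2018 | 31-AUG-2018 | in range | 31-AUG-2018 |
| 01-JUN-2018 | no | NK-AUG-2018 | 31-AUG-2018 | in range | 31-AUG-2018 |
| NK-MAR-2018 or NK-NK-2018 (set to 10-MAR-2018) | no | NK-AUG-2018 | 31-AUG-2018 | in range | 31-AUG-2018 |

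The gaps are 22 + 30 + 31 + 30 + 31 + 1 = 145 days, and 22 + 30 + 31 + 30 + 31 + 31 + 30 + 31 + 30 + 31 + 1 = 298 days.

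Three things follow:

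1. The first four records get an end date that the recorded month or year rules out. The range condition corrects all four.
2. The two truly ambiguous records (rows five and six) keep the day before first dose, so the fix does not disturb what the exception appears to be for.
3. The end-date row is out of order with itself. In row one, a wholly missing stop date would have left the drug ongoing. Recording AUG-2018, which is stronger evidence of use on study, moves the stop to before first dose.

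For deviations, D − 1 always lies within the 14 days before first dose. SAP Appendix 2 has a separate row for prohibited drugs in that window.

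**The case against.** The case against giving this much weight is good, and most of it stands.

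- **The trigger is narrow.** Drugs tagged at baseline, drugs with a start on or after first dose, and untagged drugs with a partial start whose range includes first dose all keep the upper limit. An untagged drug with a known pre-dose start and a post-dose stop month is an inconsistent record that should be queried anyway. SAP 6.2 schedules concomitant medication at screening and at the treatment-period visits, and Appendix 1 expects dates to be complete, so imputation is a fallback.
- **The consequence is conditional.** The SAP does not define prior and concomitant medication, and does not say that classification uses imputed dates.
- **A reader might infer that a prohibited drug taken on study would vanish from the deviation review.** The documents do not support this. SAP 7.4 has clinically trained personnel identify violations before database lock, and does not say that they work from imputed dates. If they did, the imputed day would fall in the 14-day pre-dose row. The drug would be moved to the wrong row, as a false eligibility breach, not lost. Both rows are case by case for the per-protocol set.
- **A reader might also infer a threat to the interaction and ECG precautions in Protocol 6.10.** Those are carried out during treatment, and a date imputed at analysis does not alter them.

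None of this defends the rule itself. For the records it does reach, it returns a date that the data exclude, against general rule 4 and out of line with two other rows of the same table.

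**Conclusion.** The end-date exception is wrong as written. For an untagged medication with a missing or pre-dose start, and a partial stop date whose month or year lies wholly after first dose, it imputes a date outside the recorded range. The size of the error is the gap from the day before first dose to the first day of that month or year: 143, 145 and 298 days in the examples, all of which use assumed first-dose dates.

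The effect on results depends on something the SAP leaves unstated. If prior or concomitant status comes from imputed dates, such use would be misclassified as prior in the SAP 7.3 summary, and a prohibited drug could be assigned to the pre-dose deviation in place of the on-study one. Neither deviation removes a patient from the full analysis set, so that set and the primary analysis are untouched. The documents do not give the number of such records. This is a small correction, worth making because the error is clear and easy to remove.

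**What to change.** In SAP Appendix 1, add to the medication end-date exception the condition that the start-date row already has, that "the treatment start day falls in the range of possible dates", and use the upper limit in all other cases. State that a medication whose earliest possible stop date is after first dose is concomitant, whatever its start date. It would help also to define prior and concomitant medication, and to say that the deviation review uses the dates as recorded.

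One boundary needs care when programming. If first dose is the first day of the recorded month or year, then L = D: the range condition is met, yet D − 1 still falls one day outside the range. Coding the condition as L < D closes that gap.

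The cost is a few lines in the SAP and one condition in the derivation program. No data collection or protocol text changes.

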3.5 Duration of study treatment (treatment phase)

The study treatment period is defined as the time elapsed between the first and the last dose of drug taken.

The study treatment should be discontinued if at least one of the reasons described in Section 3.2 occur, and the reason(s) for discontinuation will be recorded in the patient's history and in the corresponding case report form.

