3.6 Duration of post-treatment follow-up period (follow-up phase)

The follow-up period is defined as the time elapsed from the last dose of treatment received and death, withdrawal of consent or end of study (EoS), whichever occurs first.

Protocol No.: MedOPP112 Protocol date: May 21, 2018

Version 3

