5.3 Follow-up phase

Patients will be followed up until the patient dies or the study ends, whichever occurs first. The follow up of all patients will be performed until the last patient completes 78 weeks of treatment, progresses or dies, whichever occurs first.

At these follow-up contacts, information will be obtained on survival status and post-study antineoplastic therapy assessment. Contact by telephone is permitted.

Any events grade ≥2 will be followed until improvement to baseline levels is observed, complete recovery or resolution to grade 1, consent is withdrawn by the patient, patient death or until follow-up is no longer possible.

Protocol date: May 21, 2018 Version 3

 Assessment schedule after progression or study discontinuation for any reason: After progression or study discontinuation for any reason, the following assessments will be performed within a maximum period of 28 days:

- o Anamnesis and symptom assessment.
- Physical examination and measurement of weight, vital signs and ECOG performance status.
- Basic blood test that includes blood count (hemoglobin, hematocrit, RBC count, platelet count and leukocyte count with differential blood count [neutrophils, lymphocytes, monocytes, eosinophils and basophils]) and blood chemistry (sodium, potassium, calcium, chloride, magnesium, uric acid, total proteins, alkaline phosphatase, gamma-glutamyl transferase, lactate dehydrogenase and total bilirubin) with renal function analysis (serum creatinine and creatinine clearance according to the Cockcroft-Gault formula), liver function (AST, ALT, ALP and bilirubin), glucose and coagulation (INR).
- Urine dipstick test for analysis of proteinuria.
- o 12-lead electrocardiogram.
- o Blood sample, which is then sent to central laboratory.
- o Antineoplastic therapy.
- o Assessment of concomitant medications.
- Assessment of adverse events.
- o Tumor evaluation: CT, PET-CT and MRI of at least the chest and abdomen.
- Survival.
- Tumor re-biopsy will be considered (as recommendation only) for analysis of possible mechanisms of resistance and future translational research at the reference laboratory.

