6.7 Treatment compliance

At the beginning of each cycle, patients will be required to return all bottles of osimertinib (AZD9291) for drug count. The members of the study staff are responsible for counting osimertinib (AZD9291).

Drug accountability will be performed on Day 1 of every cycle prior to dispensing drug for the next cycle. The number of remaining tablets will be documented and recorded.

To be considered compliant, each study patient must have received at least 80 % of the planned number of doses of primary treatment based on the number of days of actual dose administration. If a dose titration is required, see instructions provided in section 6.9.

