5.2.2 Secondary endpoints

The following exploratory endpoints will be analysed:

- Objective response rate (ORR) is defined as the number of patients with complete response (CR) and partial response (PR) divided by the number of patients in the analysis set. Tumor response will be defined as best response, based on local investigator's assessment according to RECIST criteria guidelines (version 1.1).
- Disease control rate (DCR) is defined as the patients with CR, PR, or SD relative to all participants in analysis set. Participants who do not have on-study radiographic tumor reevaluation, who received anti-tumor treatment, who died, progressed, or dropped out for any reason prior to achieving reaching a CR or PR and a best response of SD was counted as non-responders in DCR.
- The progression-free survival (PFS) as assessed by investigator is defined as the time from the date of randomization to the date of the first documentation of objective tumor progression as per RECIST v1.1 or death due to any cause in the absence of documented PD, whichever occurs first. If tumor progression data include more than 1 date, the first date will be used. PFS (in months) will be calculated as (first event date – randomization date +1)/30.4. Progression is defined using RECIST v1.1, as a 20% increase in the sum of diameters of target measurable lesions above the smallest sum observed (over baseline if no decrease in the sum is observed during therapy), with a minimum absolute increase of 5 mm, or unequivocal progression of pre-existing non-target lesions, or the appearance of new lesions.
- Overall survival (OS) is defined as the time from treatment start to the time of death due to any cause.
- Time to treatment failure (TTF) is defined as the time from treatment start to the time at which the patient discontinues treatment due to any cause, including disease progression assessed by the investigator as per RECIST v1.1, toxicity, death or at the patient's request.
- Duration of response (DOR): is defined as the time from the date of first documented response (CR or PR that was subsequently confirmed) until the date of documented progression (PD) or death in the absence of disease progression (by investigator assessment).
- Tumor shrinkage (TS) is defined as the percentage of tumor shrinkage from baseline (obtained from the sum of the largest diameters of the target lesions) per RECIST v1.1 criteria.

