Number and percentage of patients who obtain Complete Response, Partial Response, Stable Disease and Disease Progression will be provided. The Objective Response Rate (ORR), unconfirmed and confirmed and its 95% confidence interval (CI) will be calculated. The Disease Control Rate (DCR) and its 95% CI will be calculated. Progression-free Survival (PFS), Overall Survival (OS), Time to Treatment Failure (TTF) and Duration of Response (DOR) will be considered secondary objectives, and as they are time objectives, they will be analyzed using the Kaplan-Meier method. The number and proportion of events and median survival time with their corresponding 95% CIs will be calculated. The analyses will be supported by graphical presentations such as survival plots. The average percentage of Tumor Shrinkage (TS) observed from baseline to study visits, with their corresponding 95% CIs, will be calculated.

All efficacy analyses will be exploratory. Positive results in this trial will not confirm treatment efficacy, however, they will indicate that osimertinib (AZD9291) might be considered in the supportive tests.

7.3 Safety analysis:

Analysis of safety-related data will be considered at three levels:

- First, the degree of exposure (dose, duration, number of patients) will be assessed to determine the degree to which study safety can be assessed.
- Second, clinically relevant tests, concomitant medications and reported adverse events for each study group will be described and compared. For adverse events, severity, expectedness, causality, relationship, body system, action taken and outcome will be reported.
- Third, serious adverse events, deaths and study discontinuations for each study group will be described and assessed.

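### A wholly missing end-of-treatment date is set to the earlier of last contact and death, which overstates time to treatment failure and exposure for a patient who stopped and was then followed

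*SAP*

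**What the plan says.** SAP Appendix 1 has a row for the end-of-treatment date. Both of its cells open "Use the earliest date between the". For an incomplete date the candidates are the upper limit of the possible range, the "last contact date" and the date of death. For a wholly missing date only the last two remain. Neither cell has a cap at last dose, last dispensing, progression or new therapy, and neither document defines last contact.

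Two quantities use this date. SAP 5.2.2 defines TTF as "the time from treatment start to the time at which the patient discontinues treatment due to any cause". SAP 7.3 says that "the degree of exposure (dose, duration, number of patients) will be assessed" as the first level of the safety analysis.

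The protocol separates treatment from follow-up at the last dose. Section 3.5: "The study treatment period is defined as the time elapsed between the first and the last dose of drug taken". Section 3.6: "The follow-up period is defined as the time elapsed from the last dose of treatment received and death", withdrawal of consent or end of study. Section 3.2 sets follow-up visits every 12 weeks. Section 5.3 adds: "At these follow-up contacts, information will be obtained on survival status and post-study antineoplastic therapy assessment", with telephone contact allowed. SAP Table 1 schedules these contacts up to week 78 from first dose, and Protocol 5.3 continues them until the last patient completes 78 weeks.

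**The concern.** In this trial contact continues after the last dose by design, so last contact is not a measure of when treatment ended. On its plain wording the rule counts follow-up time as treatment time for anyone who stopped and stayed in follow-up. The longer such a patient survives, the larger the error.

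The general rules in Appendix 1 widen the ways in which the row can be triggered. A date with any part out of range is treated as wholly missing, and a date with an unreadable month is reduced to the year alone. A data-entry slip is enough; the patient need not be lost.

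At stake are the Kaplan-Meier summary of TTF and the duration of exposure against which safety is read. Better evidence is already gathered. Protocol 6.7 states: "Drug accountability will be performed on Day 1 of every cycle prior to dispensing drug for the next cycle".

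**Working it through.** The plan states no figure for the effect of this rule, so there is none to reproduce. The rule is applied directly.

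**Inputs from the documents**
- Imputed end of treatment = min(last contact, death): SAP Appendix 1.
- Off-treatment contacts at weeks 12, 24, 36, 48, 60, 72 and 78 from first dose: SAP Table 1.
- Visits every 6 weeks: Protocol 5.2. Supply of 21 + 4 days per cycle until the next visit: Protocol 6.4.

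**Step 1. One patient, date wholly missing, last contact at week 78.** Overstatement = 78 − true stopping week. Months = weeks × 7 / 30.4, the SAP's own divisor for PFS.

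| True stop (week) | Overstatement (weeks) | Months |
|---|---|---|
| 6 | 72 | 16.6 |
| 12 | 66 | 15.2 |
| 20 | 58 | 13.4 |
| 24 | 54 | 12.4 |
| 36 | 42 | 9.7 |
| 48 | 30 | 6.9 |

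The death limb limits this little, because a patient's last contact normally precedes death.

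**Step 2. Incomplete dates.** If only the day is missing, the upper limit is the end of the known month, so the error is at most 30 days. If only the year is known, the upper limit is 31 December, so the error can reach 364 days (365 in a leap year), unless last contact or death comes sooner.

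**Step 3. Patient lost while on treatment.** Last contact is then an on-treatment visit. Supply handed out for two cycles is 2 × (21 + 4) = 50 days, about 7.1 weeks. The patient may dose for up to that long after last contact, so here the rule can understate treatment duration.

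**Step 4. Effect on group summaries.** This step rests on assumptions, because the documents give neither the missing fraction nor the distributions. TTF was taken as exponential with median 26, 52 or 78 weeks, and survival after stopping as exponential with median 52 weeks. Contacts follow SAP Table 1 to a 78-week horizon, with N = 21 or 73 and 1,500 simulated trials per setting. Dates go missing at random among patients who stopped before week 78, and all survival contacts count as last contact. The mean overstatement per affected patient is about 28 to 34 weeks.

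| Missing dates (assumed) | Rise in median TTF (weeks) | Rise in mean exposure (weeks) |
|---|---|---|
| 2% | 0.6 to 1.1 | 0.3 to 0.6 |
| 5% | 1.5 to 2.4 | 0.7 to 1.5 |
| 10% | 3.2 to 5.0 | 1.5 to 3.0 |
| 20% | 7.1 to 10.8 | 2.8 to 5.8 |

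The shift in the median is averaged over simulated trials in which the median was reached both with true and with imputed dates. It is therefore least reliable for the 78-week setting.

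**Step 5. How many patients.** SAP section 9 reports that accrual closed after the interim analysis, which was planned at 21 patients. The final number is not given. If it is about 21 and 1% to 5% of dates are missing (assumed), the expected number affected is 21 × 0.01 = 0.2 to 21 × 0.05 = 1.1. The chance that nobody is affected is 0.99^21 = 0.81 to 0.95^21 = 0.34. One patient in 21 is 4.8%.

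**The case against.** The strongest reply is that the harmful case is rare. It needs a patient known to be off drug and contacted for months, yet with no usable stop date. The reason for discontinuation goes into the case report form, as do dose changes and interruptions. Tablets are counted, and an end-of-treatment assessment falls within 28 days. Appendix 1 gives patients lost to follow-up as its example of missing dates; for someone lost while on treatment, last contact is a fair proxy. The authors may have meant last on-treatment contact. All of this bears on how often the rule does harm, and it stands. It does not change the value that the rule returns when a patient has stopped and been followed, and the SAP does not state the narrower meaning.

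A reader might also infer more than the documents support:

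- *That the error always lengthens treatment.* Step 3 shows that it can go the other way for a patient lost with tablets in hand.
- *That the adverse-event window of 28 days after last dose is distorted.* The footnote to SAP Table 1 tells sites what to record. Nothing in the SAP filters events by an imputed end-of-treatment date.
- *That TTF is overstated for every affected patient.* The TTF definition counts investigator-assessed progression among the causes of failure, so a documented progression date may govern. The SAP does not say which date takes precedence. Exposure has no such protection.
- *That every incomplete date shares the problem.* Only the year-only case can be large.

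**Conclusion.** The point holds for patients known to have stopped treatment and then followed. For them, the rule as worded overstates exposure duration, and also TTF unless a documented progression date governs. The error can exceed a year for one patient: 58 weeks for a stop at week 20 and last contact at week 78.

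The likely effect on group summaries is modest. At 2% to 5% missing, median TTF would move by roughly 0.6 to 2.4 weeks under the assumptions of Step 4. The true number of missing dates is unknown and probably low. In a group of about 21, though, a single one is already near 5%.

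The primary confirmed response rate and the two-stage decision rule are untouched. TTF is a secondary, exploratory single-arm summary. This is nevertheless more than a missing definition: a stated rule returns a wrong value when triggered, and a better source is already recorded. The conclusion rests on reading last contact to include survival contacts, which is its plain meaning here.

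**What to change.** Replace the end-of-treatment row in SAP Appendix 1 with the following.

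- For patients known to have stopped: impute the last date supported by dosing evidence (last tablet count, or last dispensing date plus the supply dispensed). Go no later than the earliest of documented progression leading to discontinuation, start of new antineoplastic therapy, last contact and death.
- Apply the same cap to incomplete dates.
- For patients not known to have stopped: do not impute a stop; censor at the last on-treatment contact.
- Define last contact for this row, state whether a documented progression date governs TTF, and list every imputed date.

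The cost is one table row plus a listing. Protocol 6.7 says that tablet counts are recorded but not that they enter the case report form, so check first that they are in the database.

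The downside is a residual error of up to about one dispensing interval per affected patient. That is 6 weeks between visits, or 50 days (7.1 weeks) of supply, against up to 72 weeks now for a stop at week 6 and last contact at week 78. This error no longer grows with survival follow-up.
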